### **Other Outcome Measures:**

- spontaneous opioid craving, assessed using the Penn Alcohol-Craving Scale, as modified to assess opioid craving
- affect, assessed using the Positive and Negative Affect Schedule (PANAS)
- anxiety assessed by State subscale of the Spielberger State-Trait Anxiety Inventory
- blood pressure, heart rate, and respiratory rate during the laboratory sessions
- Plasma levels of CBD
- plasma levels of buprenorphine

**Participant Recruitment:** Patients will be recruited from the Tarzana Treatment Center in the San Fernando Valley (TTC), where buprenorphine or methadone (as part of their treatment) and CBD (as part of this protocol) will be administered.a Tarzana Treatment Centers, Inc. is a community-based, private non- profit behavioral healthcare organization located in Southern California with several agency sites, including the one in the San Fernando Valley, where this protocol will be conducted.

TTC delivers drug and alcohol use treatment, has been accredited by the Joint Commission on Accreditation of Healthcare Organizations (JCAHO) since 1987, and has a workforce that includes physicians, psychologists, and nurses. TTC's substance use treatment approach includes residential programs that are overseen by a Program Director and are staffed by a clinical supervisor, operations supervisor, counselors, interns, nursing staff and 24/7 technicians. Groups and services include education group, process group, 12-step, family group, mental health services and recreation skills. Cognitive-behavioral treatment is used in both individual and group therapy to address craving and relapse issues and in the treatment of mental health problems.

**Randomization to Treatment:** Up to 60 patients who meet all eligibility criteria will be randomized to receive CBD or placebo (up to 30 patients per group): CBD 600 mg/day (300 mg twice daily). Within each cohort, patients will be randomized by baseline plasma buprenorphine level (either below or  $\geq$  2 ng/mL)

**Dosing and Testing Schedule:** The study will comprise three periods: a 14-day screening period while patients are stabilized on buprenorphine), a 28-day treatment period (CBD 600 mg/day or placebo), and a 28-day follow-up period after termination of treatment with medication.

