**Study Periods:** The study design comprised four phases: 1) a 14-day screening period during which patients were consented, evaluated against entry criteria, and stabilized on buprenorphine; 2) randomization and baseline evaluation (Day 0); 3) a 28-day acute treatment period when each participant received the IMP twice daily (CBD or placebo); primary data collection phase, and 4) a 28-day follow-up period after termination of treatment with study medication (secondary data collection phase). Safety assessments included clinical lab tests during screening and weekly during the treatment and follow-up periods. On each study day, vital signs were taken, and patients reported adverse events, which were monitored and recorded. Although not a direct measure of safety, change in buprenorphine metabolism, operationalized as the ratio of buprenorphine to norbuprenorphine in plasma, was obtained, as out of range values occurring in the context of hypoxia and/or sedation could be indicative of increased risk. Because CBD inhibits CYP3A, the primary mechanism for hepatic buprenorphine N-dealkylation, the buprenorphine to norbuprenorphine ratio was measured in blood drawn for relevant PK analyses at baseline and weekly during the treatment and follow-up periods. Cue-induced craving was measured in laboratory sessions with a paradigm in which neutral and opioid-related cues were presented. These sessions were conducted before dosing on Day 0 (Baseline) and on Days 7 and 28 after study drug initiation (Treatment Phase).

The original protocol was approved by the FDA on October 12, 2020 (IND 152888). Modifications were needed because the approved investigational product became unavailable. On October 27, 2021, the FDA approved using ATL5 (100 mg/ml CBD softgel capsules) and matching placebo as the investigational medicinal products (IMPs), and testing two ascending-dose cohorts [cohort 1: CBD 600 mg/day, N = 20 and placebo (N = 10); cohort 2: CBD 1200 mg/day, N = 20 and placebo, N = 10)], each randomized 2:1 CBD:placebo, with the combined placebo subsamples intended to be treated as a common reference for both drug groups. The trial commenced in March 2022.

[figure not shown]
Randomization was stratified by baseline (i.e. post-stabilization period) plasma buprenorphine level—either < 2 ng/mL or ≥ 2 ng/mL—measured immediately prior to randomization and the daily dose of buprenorphine.

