### 3.5. Sample Size

Sample size is based on the change in cue-induced craving from baseline to 28-days, the end of the acute treatment period. The actual number of subjects enrolled has changed since the initial protocol. This section will focus on the standardized effect size needed to show 1-sided significance level of  $\alpha = 0.025$  (equivalent to  $\alpha = 0.05$  two sided but reflecting our directional hypothesis), based on 21 treated and 14 placebo subjects. Based on the SAS power calculation below, if there is a standardized effect size of  $d = 1.0$ , then there is a power of 0.80.

```
proc power;  
  twosamplemeans test=diff  
  groupmeans = 0 | 1  
  stddev = 1
```

```
groupweights = (14 21)
ntotal = 35
power =. ;
run;
```

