### **Primary Efficacy Target**

**Desire for Drug Questionnaire (DDQ):** The DDQ is a 14-item scale used to assess cue-induced craving, administered here in the context of a laboratory-based opioid cue-induction paradigm. All responses are scored on a Likert scale from "strongly disagree" (1) to "strongly agree" (7). A table will be provided with summaries per visit (Baseline, 7, and 28 days), as well as absolute and percent changes from baseline, for the DDQ Total Score of Opiate Use (subscale including 7 items, primary endpoint) and the DDQ Total Score (all 14 DDQ items, secondary endpoint), both of which will be used to assess cue-induced craving, our primary efficacy target. For each outcome, we will run a mixed model for repeated measures (MMRM), with change from baseline as the outcome; fixed effects for treatment, time, and a treatment by time interaction; and an appropriate random effects/covariance structure to account for within-subject correlations. In addition, figures, based on the MMRMs will be provided: 1) by treatment, and 2) for the difference between treatments, both with 95% model estimate confidence intervals. The primary efficacy outcome is the MMRM model estimate for change from baseline in cue induced craving at 28 days between the two treatment groups.

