## 12. Pharmacokinetic Analyses and Effect on Endogenous Cannabinoids

All pharmacokinetic analyses will be performed using nominal times due to the limited amount of actual time data available.

Noncompartmental analysis (NCA): On Day 0, 14, and 28, the following NCA parameters will be calculated for CBD and its metabolites: Cmax, Tmax, and AUC0-24. Half-life will be estimated on Day 28, as data permit. Time to steady-state will be evaluated graphically based on trough concentrations. Accumulation ratios for Cmax and AUC0-24 will be estimated on Days 14 and 28 relative to Day 0.

Buprenorphine (bup) and norbuprenorphine (norBup) NCA parameters of Cmax, Tmax, and AUC0-24 will be calculated on Day 0, 14, and 28.

Bup and norBup drug interaction assessment: Bup and norBup Cmax and AUC0-24 accumulation ratios (geometric mean ratios) will be estimated for those who do and do not receive CBD to assess the potential for drug interactions. We will then use an ANCOVA model with body weight as a covariate to compare the groups. Any patient who changed Bup dose during the study will not be included in drug interaction evaluations.

In exploratory analyses, to determine whether treatment with CBD affects plasma concentrations of anandamide and 2-AG, we will run separate MMRM analyses with group (600 mg CBD or placebo), time and their interaction as predictors and changes in anandamide and 2-AG as the dependent variables, respectively.

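### The stratification factors used at randomisation are in neither the DDQ model nor the buprenorphine interaction ANCOVA; adding them costs almost nothing and recovers precision if they predict the outcome

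*SAP*

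**What the plan says.** **Randomisation.** SAP 3.1 states: "Randomization was stratified by baseline (i.e. post-stabilization period) plasma buprenorphine level", with a cut at 2 ng/mL. The sentence goes on to say that the level was "measured immediately prior to randomization and the daily dose of buprenorphine". As worded, that makes daily dose a second stratification factor, and no dose cut-points are given. The protocol, under Randomization to Treatment, says that within each cohort "patients will be randomized by baseline plasma buprenorphine level", with the same 2 ng/mL cut. It does not mention dose.

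**Primary efficacy model.** SAP 11 (Primary Efficacy Target) specifies an MMRM "with change from baseline as the outcome" and "fixed effects for treatment, time, and a treatment by time interaction". The Day 28 contrast between arms is the primary efficacy result.

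**Interaction model.** SAP 12 compares buprenorphine and norbuprenorphine accumulation ratios between arms: "We will then use an ANCOVA model with body weight as a covariate to compare the groups".

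No section of either document puts a stratification factor into a model or explains leaving it out. SAP 13 lists no changes to the planned analysis.

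**The concern.** Stratified allocation balances the arms within each stratum, so differences between strata largely drop out of the treatment contrast. A model without the stratum still counts those differences as residual error. If the stratum is prognostic, the reported standard error then exceeds the true sampling variability, the 95% intervals are too wide, and the test runs below its nominal level.

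The trial has little precision to spare. SAP 3.5 needs a standardised effect of 1.0 and all 35 randomised participants to reach power 0.80. SAP 3.1 reports that 6 of the first 28 randomised received no study drug. They fall outside the full analysis set, so at most 35 − 6 = 29 can be analysed.

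**Working it through.** **Inputs from SAP 3.5:** 21 CBD and 14 placebo; SD 1; difference 1 ("groupmeans = 0 | 1"); one-sided alpha 0.025, which the SAP equates with two-sided 0.05.

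**Assumed, because the documents give no figure:** R², the share of variance in DDQ change explained by the stratum, taken from 0 to 0.20; two strata, allocated 9:6 and 12:8, so that each keeps the 3:2 ratio. The Day 28 contrast is treated as a single comparison, as in the SAP's own power calculation.

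**Step 1. Reproduce the stated power.**

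- Standard error = √(1/14 + 1/21) = √0.1190 = 0.345.
- Noncentrality = 1/0.345 = 2.90; df = 14 + 21 − 2 = 33.
- Noncentral t power = 0.803, which matches the stated 0.80. This calculation uses no stratum.

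**Step 2. Put the stratum in.** The residual SD becomes √(1 − R²) and df falls to 32. At R² = 0.10 the standard error is multiplied by √0.90 = 0.949, the noncentrality is 2.90/0.949 = 3.06, and power is 0.842. The same formula gives 0.802 at R² = 0, 0.822 at 0.05 and 0.881 at 0.20.

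**Step 3. Simulate both models** (40,000 trials per setting, two-sided 0.05, total SD 1).

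| Assumed R² | Power without stratum | Power with stratum | Difference (points) | Type I error without | Type I error with |
|---|---|---|---|---|---|
| 0 | 0.805 | 0.804 | −0.1 | 0.051 | 0.051 |
| 0.05 | 0.809 | 0.823 | 1.4 | 0.045 | 0.050 |
| 0.10 | 0.815 | 0.843 | 2.8 | 0.040 | 0.052 |
| 0.20 | 0.827 | 0.882 | 5.5 | 0.029 | 0.052 |

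The mechanism shows in the standard errors under the null. At R² = 0.10 the unadjusted model reports 0.343 on average, against a true sampling SD of 0.329. At R² = 0.20 it reports 0.345 against 0.310.

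**Step 4. Allow for the 6 untreated participants.** Start from the same balanced 35 and drop 6 at random, leaving 29 (8,000 trials per setting).

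| Assumed R² | Power without | Power with | Type I error without | Type I error with |
|---|---|---|---|---|
| 0 | 0.710 | 0.706 | – | – |
| 0.10 | 0.729 | 0.761 | 0.041 | 0.050 |
| 0.20 | 0.730 | 0.809 | 0.033 | 0.049 |

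The pattern survives. Random loss from balanced strata does not remove enough balance to change it.

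**ANCOVA.** The SAP states no power, variance or effect size for the interaction comparison, so no corresponding calculation was made.

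**The case against.** **The loss is conditional.** A reader might infer that the planned standard errors are too large and that power is lost outright. The documents do not support that: it follows only if the stratum predicts the outcome, and neither document reports the association. At R² = 0 the two models perform alike. This stands, and the conclusion is worded accordingly.

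**Prognostic value for change may be weak.** The DDQ outcome is a change score, so a stable difference in craving between strata is already subtracted. The accumulation ratios are relative to Day 0, so baseline exposure is partly divided out. This also stands. R² could be small, and at 0.05 the cost is only 1.4 points.

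**The protocol's remarks on receptor occupancy do not settle it.** A reader might infer from the inclusion-criteria section that plasma level was chosen as stratifier because it tracks occupancy and withdrawal. That text explains the eligibility dose range. It does not mention randomisation, and it does not link plasma level to craving. Neither document says why the stratifier was chosen.

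**Balance may not hold in the analysed sets.** The full analysis set drops untreated participants, and the ANCOVA drops anyone whose buprenorphine dose changed. Step 4 shows that random loss of 6 leaves the result intact. Loss related to both stratum and arm is not covered by that check, but the imbalance it would create is itself a reason to adjust.

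**The consequence is mild.** The unadjusted test is conservative: false positives are not inflated and, with strata balanced, the estimate is not biased. Craving is also the secondary objective. Losing participants probably costs more: with 29 treated in an assumed 17:12 split, the SAP's own t-test has power 0.725. All of this is correct and limits how much weight the point carries. But the lost participants cannot be recovered, whereas this precision can.

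**Conclusion.** The omission from both models is a fact of the documents, and it is unexplained. Its consequence for the DDQ analysis depends on how well the stratum predicts change. Power lost is nil at R² = 0, under 3 points for R² up to 0.10, and about 5.5 points at 0.20, with type I error falling to about 0.040 and 0.029 at the last two values. These figures rest on assumed R², balanced strata and the SAP's 21 versus 14 at d = 1.0. For the ANCOVA the direction would be the same, but the gain is unquantified and less certain.

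The SAP and the protocol also differ on whether daily dose was a stratification factor, and this has to be settled before the models can be completed. The planned test is not invalid; this is a free improvement, worth making because adjusting costs almost nothing even if the stratum proves uninformative.

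**What to change.** Before unblinding:

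1. Reconcile SAP 3.1 with the protocol's Randomization to Treatment paragraph. State which factors the randomisation actually used and, if daily dose was one, its categories.
2. Add to SAP 11: *All MMRMs include the randomisation stratum (baseline plasma buprenorphine <2 vs ≥2 ng/mL, as used at randomisation, and any daily-dose stratum actually used) as a fixed effect.*
3. Add the same factor or factors to the ANCOVA in SAP 12.

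If a factor is left out on purpose, say why. The cost is one degree of freedom for the plasma-level factor, slightly more if a dose stratum was used, and no new data. Timing matters because adding the factors after unblinding would be post hoc.

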### **Secondary Efficacy Outcomes**

**Clinical Opiate Withdrawal Scale (COWS):** The COWS is an 11-item measure of opiate withdrawal with Likert-type responses ranging from 0 to 5 or 0 to 4, depending on the particular item. There is no reverse scoring. The total COWS score is taken as the sum of all items. A table and plots similar to those for DDQ will be created encompassing all the available visits (Baseline to Day 33) for the COWS total measurement.

**Penn Alcohol Craving Scale (PACS; adapted for opioid craving):** The PACS is a 4-item scale to assess spontaneous craving with Likert-type responses ranging from 0 to 6. PACS summary scores will be calculated by summing the responses on all 4 items since no reverse scoring is required. Tables and plots will be provided as above.

**State Trait Anxiety Inventory (STAI); State Scale:** The STAI State scale is a 20-item measure of state anxiety with Likert-type responses ranging from "not at all" (1) to "very much so" (4). For half of the items (items 1, 2, 5, 8, 10, 11, 15, 16, 19, and 20), reverse scoring is required in which case the responses range from "not at all" (4) to "very much so" (1). After reverse scoring, all 20 items are summed to provide a total score. Tables and plots will be provided as above.

**Positive and Negative Affect Schedule (PANAS)-Positive Affect Scale:** There are 30 items on the PANAS with Likert-type responses ranging from "Very Slightly or Not at All" (1) to "Extremely" (5). There is no reverse scoring. For the PANAS Positive Affect Scale, 15 items are summed: #'s 1, 2, 5, 6, 7, 13, 14, 15, 17, 19, 21, 24, 25, 26, and 28. Tables and plots will be provided as above.

**Positive and Negative Affect Schedule (PANAS)-Negative Affect Scale:** There are 30 items on the PANAS with Likert-type responses ranging from "Very Slightly or Not at All" (1) to "Extremely" (5). There is no reverse scoring. For the PANAS Negative Affect Scale, 15 items are summed: #'s 3, 4, 8, 9, 10, 11, 12, 16, 18, 20, 22, 23, 27, 29, and 30. Tables and plots will be provided as above.

## 12. Pharmacokinetic Analyses and Effect on Endogenous Cannabinoids

All pharmacokinetic analyses will be performed using nominal times due to the limited amount of actual time data available.

Noncompartmental analysis (NCA): On Day 0, 14, and 28, the following NCA parameters will be calculated for CBD and its metabolites: Cmax, Tmax, and AUC0-24. Half-life will be estimated on Day 28, as data permit. Time to steady-state will be evaluated graphically based on trough concentrations. Accumulation ratios for Cmax and AUC0-24 will be estimated on Days 14 and 28 relative to Day 0.

Buprenorphine (bup) and norbuprenorphine (norBup) NCA parameters of Cmax, Tmax, and AUC0-24 will be calculated on Day 0, 14, and 28.

Bup and norBup drug interaction assessment: Bup and norBup Cmax and AUC0-24 accumulation ratios (geometric mean ratios) will be estimated for those who do and do not receive CBD to assess the potential for drug interactions. We will then use an ANCOVA model with body weight as a covariate to compare the groups. Any patient who changed Bup dose during the study will not be included in drug interaction evaluations.

In exploratory analyses, to determine whether treatment with CBD affects plasma concentrations of anandamide and 2-AG, we will run separate MMRM analyses with group (600 mg CBD or placebo), time and their interaction as predictors and changes in anandamide and 2-AG as the dependent variables, respectively.

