### 3.4. Objectives and Endpoints

Objectives	Endpoints
Primary: To evaluate the safety and tolerability of CBD in the study population.	Primary: Number of treatment-emergent adverse events over the 28-day treatment period by study arm. Secondary: Changes in liver enzymes, pulse oximetry, sedation, and cardiovascular measures (heart rate, blood pressure, and cardiac rhythm and conduction on EKG).
Secondary: To determine the extent to which CBD (600 mg/day) reduces cue-induced craving for opioids relative to placebo.	Primary: Cue-induced craving for opioids, assessed using the Desires for Drug Questionnaire (DDQ)  in the context of an opioid cue-induction paradigm, assessed in the laboratory session before CBD dosing on Day 0 (baseline without CBD) and on Days 7 and 28 (after adjunctive treatment with CBD) Secondary: Spontaneous opioid craving, assessed using the Penn Alcohol-Craving Scale, as modified to assess opioid craving;  affect, assessed using the Positive and Negative Affect Schedule (PANAS),  Anxiety, assessed by state subscale of the Spielberger State-Trait Anxiety Inventory,  Percentage of patients with increase in their buprenorphine dose, Treatment retention, as indicated by number of days of continued participation
Exploratory: A. To evaluate effects of CBD on metabolism of other endocannabinoids, i.e., N-arachidonylethanolamide (anandamide) and 2-arachidonoyl-glycerol (2-AG) levels. B. To assess pharmacokinetics of CBD in patients receiving buprenorphine for treatment of OUD.	Plasma levels of anandamide and 2-AG. CBD pharmacokinetics—time to reach steady state and accumulation parameters (C max , AUC 0-24 ). In addition, the buprenorphine/norbuprenorphine ratio will be determined to evaluate potential drug-drug interactions of CBD with buprenorphine metabolism (dealkylation). Although this ratio does not, by itself, an increase in the ratio, concurrent with the emergence of hypoxia and/or sedation would be an AE.

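### The buprenorphine dose-change exclusion in SAP section 12 can discard unaffected PK profiles, and no summary, model or interval is planned for the buprenorphine/norbuprenorphine ratio

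*SAP*

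**What the plan says.** **Exclusion.** SAP section 12 calculates buprenorphine and norbuprenorphine Cmax, Tmax and AUC0-24 on Days 0, 14 and 28. For the interaction, "Bup and norBup Cmax and AUC0-24 accumulation ratios (geometric mean ratios) will be estimated for those who do and do not receive CBD", and the groups are then compared by ANCOVA with body weight as covariate. The paragraph ends: "Any patient who changed Bup dose during the study will not be included in drug interaction evaluations". It does not say which days count, and it plans no sensitivity analysis and no count of exclusions by arm. SAP section 3.1 makes "a 28-day follow-up period after termination of treatment with study medication" one of the study's phases. SAP section 3.4 lists as an endpoint "Percentage of patients with increase in their buprenorphine dose".

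**Ratio.** The protocol (Study Objectives) places the interaction in the primary objective and predicts that CBD will raise the buprenorphine/norbuprenorphine ratio. SAP section 3.1 describes "change in buprenorphine metabolism, operationalized as the ratio of buprenorphine to norbuprenorphine in plasma", "measured in blood drawn for relevant PK analyses at baseline and weekly during the treatment and follow-up periods", with the reservation "Although not a direct measure of safety". SAP section 3.4 lists the ratio under an exploratory objective as the means of evaluating the interaction. Section 12 does not mention it.

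**The concern.** A dose change before a PK day confounds a comparison with Day 0, so excluding that patient has a sound pharmacokinetic reason. A dose change after a PK day cannot affect the profile already taken, yet the rule deletes that profile too. At most 29 participants were dosed, so avoidable losses deserve attention.

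The excluded event also occurs after randomisation, and when it is an increase it is itself an endpoint. If CBD influences who changes dose, the remaining patients in the two arms may no longer be comparable. Without counts by arm the reader cannot judge this.

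For the ratio, the measure that carries the protocol's prediction would reach the report without a planned estimate of uncertainty. The SAP Introduction requires any unplanned analysis to be labelled as such, so an interval added after unblinding would be post hoc.

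**Working it through.** The plan gives no power or precision figure for the interaction analysis. Its only power figure (0.80, SAP section 3.5) concerns craving and has no bearing here.

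**Step 1. What each reading of the exclusion removes**

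| Dose change occurs | Profile unaffected by it | Literal reading | Treatment-phase reading |
|---|---|---|---|
| Day 0 to Day 14 | none after baseline | excluded | excluded |
| Day 14 to Day 28 | Day 14 | Day 14 lost | Day 14 lost |
| After Day 28 | Days 14 and 28 | both lost | both kept |

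Day 28 is the last NCA day, not the last buprenorphine sample: section 3.1 has ratio sampling weekly through follow-up. Follow-up changes are foreseeable. Protocol Table 1 requires a stable dose only through the treatment phase, and Duration of Treatment and Dropout puts the inpatient stay at about one month, with buprenorphine often continued afterwards.

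**Step 2. Size of the loss (illustrative)**

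From SAP section 3.1: dosed at most 28 − 6 + 7 = 29, fewer on buprenorphine if some took methadone. If the 6 undosed follow the 2:1 allocation, CBD is 22 × 2/3 + 7 × 1/3 = 17 and placebo 22 × 1/3 + 7 × 2/3 = 12.

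Assumed, because the documents give neither: a share q changes dose, evenly over Days 1 to 56 and alike in both arms; log-SD 0.3.

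Patients removed: literal rule 29q; changes up to Day 28 only, 29q × 28/56; changes up to Day 14 only, 29q × 14/56.

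95% CI factor = exp( t(0.975, n − 3) × SD × √(1/n1 + 1/n2) ).

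For q = 20%, literal rule: 5.8 removed, expected arms 13.6 and 9.6, t = 2.085, standard error 0.1265, factor exp(0.264) = 1.30. Limited at Day 28: 2.9 removed, arms 15.3 and 10.8, t = 2.068, standard error 0.1192, factor exp(0.247) = 1.28.

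| q | Literal: removed, factor | Limited, Day 28 | Limited, Day 14 |
|---|---|---|---|
| 10% | 2.9, 1.28 | 1.5, 1.27 | 0.7, 1.27 |
| 20% | 5.8, 1.30 | 2.9, 1.28 | 1.5, 1.27 |
| 30% | 8.7, 1.33 | 4.3, 1.29 | 2.2, 1.27 |

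With no exclusion the factor is 1.26. On the treatment-phase reading with q = 20%, the current rule removes 2.9 patients from the Day 14 comparison and the limited rule 1.5 (1.28 against 1.27). At Day 28 the two rules agree.

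**Step 3. Do equal exclusion rates make bias cancel?**

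Not necessarily. Extreme illustration: no true effect, log-SD 0.3, 20% removed from each arm, the highest values in one and the lowest in the other. Each mean shifts by 0.3 × 0.280/0.8 = 0.105 in opposite directions, so the geometric mean ratio becomes exp(−0.21) = 0.81. Cancellation needs the same kind of selection in both arms, not only the same rate.

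**Step 4. What the separate analyses give for the ratio**

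On the log scale, with the same patients and covariates, the ratio contrast equals the buprenorphine contrast minus the norbuprenorphine contrast. Its variance also needs the within-patient correlation r. With equal log-SDs, SD(log ratio) = SD × √(2(1 − r)). With 17 and 12 patients, t = 2.056:

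| log-SD | r = 0 | r = 0.5 | r = 0.8 |
|---|---|---|---|
| 0.2 | 1.25 | 1.17 | 1.10 |
| 0.3 | 1.39 | 1.26 | 1.16 |
| 0.5 | 1.73 | 1.47 | 1.28 |

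At log-SD 0.3 the factor can be anywhere from 1.39 to 1.16 depending on r, so the planned output does not determine the interval.

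**The case against.** **The exclusion wording may be meant narrowly.** The sentence closes a paragraph about Days 0, 14 and 28, so the period meant could be the treatment phase. If so, the follow-up loss disappears. The Day 14 loss from a change between Days 14 and 28 remains, and the wording still needs a window.

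**The gain is small.** This stands. The confidence factor moves by 0.04 or less in every case tabulated, and the dose-change rate is assumed.

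**The ratio is exploratory and section 3.1 limits its safety role.** Also true. But section 12 gives anandamide and 2-AG, equally exploratory, a mixed model with named terms, so exploratory status does not explain the silence on the ratio.

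**Stronger readings that the documents do not support.** A reader might infer that no interaction analysis is planned. That is wrong: the two ANCOVAs test for one and, if run on the log scale in the same patients, imply the ratio's point contrast. A reader might infer that the exclusion biases the result in a known direction. The documents give no dose-change rate and nothing that fixes a direction. A reader might also infer that a ratio analysis must be more powerful. With equal log-SDs, if a fraction f of the log effect falls on buprenorphine, the ratio does better than buprenorphine alone only when r exceeds 1 − 1/(2f²): 0.11 at f = 0.75 and 0.50 at f = 1. The documents give neither f nor r.

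**Conclusion.** The point holds in two limited parts.

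First, the exclusion is wider than its pharmacokinetic reason. On any reading that covers the treatment phase it can delete an unaffected Day 14 profile; read literally, it can also delete unaffected Day 28 profiles. The precision cost is modest under the assumed inputs. Selection on a post-randomisation event is possible, with unknown direction and size, and equal exclusion rates by arm would not rule it out.

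Second, the ratio that the protocol predicts will rise, and that the SAP uses to express change in metabolism, has no planned summary, model or interval. The interval is the main gap.

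The figures rest on an assumed 17/12 split of at most 29 dosed participants, evenly spread dose changes, and assumed log-SDs and correlations. The wording gap and the missing interval do not depend on them. Severity: minor to should-fix.

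**What to change.** 1. **Exclusion.** For each NCA day, exclude only patients whose buprenorphine dose changed between the baseline profile and that day. Keep the current full exclusion as a sensitivity analysis. Report dose changes and PK exclusions by arm, direction and study day. This does not remove selection for changes before the PK day, and the report should say so.

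2. **Ratio.** Before unblinding, pre-specify an exploratory between-arm ANCOVA of the log buprenorphine/norbuprenorphine AUC0-24 ratio at Days 14 and 28, with a 95% confidence interval, adjusted for body weight and a baseline log ratio. Name the baseline sample and take it from before the first CBD dose, for example the Day −7 buprenorphine PK sample or the Day 0 pre-dose sample. Section 12 computes CBD parameters on Day 0, so the Day 0 AUC0-24 may not be CBD-free.

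3. **Analysis sets.** Use the dose-stable set as the main analysis. A run in all buprenorphine-treated PK participants is supportive only: it assumes that both analytes scale similarly with dose and are at steady state after any change, which the documents neither support nor refute.

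Cost: SAP wording and modest extra PK programming. The samples and assays are already planned.
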